### 6.3.2 Informed Consent

Please see attached informed consent in IRB submission

### 6.3.3 Screening

Patients will be identified by the sleep clinic coordinator and/or the sleep physician after their initial consult. Eligible patients must be aged between 22-64 years, English speaking, and have a diagnosis of chronic insomnia (see inclusion/exclusion criteria above in section 5.3.2). If they are interested clinic staff will notify the RA. Additionally, the patient will be provided with the study team's contact information if they wish to follow up. Eligibility will be determined by the sleep physician or coordinator stating that the patient is being seen for insomnia. The RAs will approach the patient for consent into the study while they are waiting for their sleep consult appointment/referral to see the sleep specialist. The wait time between enrollment and follow

up with sleep specialist is up to 12 weeks; therefore, this is a prime opportunity for patient enrollment and completion of this project.

The RA will also reach out to patients on the waitlist for in-person CBT-I upon the sleep clinician's approval. If the patient is interested in the study, the RA will attempt to arrange an in-person visit to conduct the consent and enrollment process. If an in-person visit is not possible, the RA will arrange a time for a Zoom call with the patient.

Additionally, a flyer will be circulated to the Sleep Clinic staff to provide to any patients who may express interest in the study (Appendix 7).

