### 3.2.1 Potential Risks

In following some intervention recommendations, participants may be asked to restrict sleep at certain times, which could lead them to initially feel more tired. This could potentially exacerbate the fatigue or sleepiness that many participants may already be experiencing. The therapeutic will direct patients to discontinue sleep restriction if they feel excessively tired.

The risk to patient privacy is no different with this study than it is with any other study that securely collects and appropriately stores personally identifiable information or protected health information. Indeed, the risk may be less since researchers are only getting access to patient data from the time of enrollment forward for 63 weeks for this study; there is no open access to the patient's entire medical record. The Hugo platform, like many other personal health records, is not a covered entity; therefore, the HIPAA privacy rule does not apply to this platform. The Hugo platform does take all necessary precautions, including industry-standard encryption, to minimize privacy and security risks to personally identifiable information stored on behalf of study participants. Hugo makes publicly available its Security Statement (<http://hugophr.com/security>), its Privacy Notice (<http://hugophr.com/privacy-notice>), and Terms of Service (<http://hugophr.com/terms-of-service/>)

Participants will undergo the possible inconvenience of filling out electronic patient-reported outcome measure surveys, which can take up to 60 minutes at each time point (at baseline, 9, 21, 35, and 61 weeks post-randomization). Additionally, some participants may feel uncomfortable providing data over the phone and have concerns about the confidentiality of their digital data. They may also have concerns about the legitimacy of a digital therapeutic. Patients will be provided the sleep clinic contact information in case they feel they need to seek support at enrollment in addition to the completion of each PHQ-8 questionnaire. The PHQ-8 is a validated measure for depression that was modified from the original PHQ-9 to not include a question about suicidality and has been used in prior studies.

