### 5.3.2 Eligibility Criteria/Vulnerable Populations

Inclusion Criteria:

- Age between 22-64 years
- English-speaking (both reading and writing in English required)
- Diagnosis of chronic insomnia
- Participant is willing and able to give consent and participate in study
- Participant has an email account or is willing to create one and a smartphone able to download the necessary applications
- Participant is willing and able to use the PDT, the Hugo data sharing platform and the syncable devices (e.g. Fitbit)
- Participant has primary care at YNHH or Mayo Clinic

Exclusion Criteria:

- Pregnancy
- Shift work or family/other commitments that interfere with establishment of regular night-time sleep patterns, and if wake/sleep time is outside the ranges of 4:00h – 10:00h (wake time) and 20:00h – 02:00h (bed time)
- Absence of a reliable internet access and smartphone
- A reported diagnosis of psychosis, schizophrenia or bipolar disorder, or any medical disorders contraindicated with sleep restriction
- Current involvement in a **non-medication** treatment program for insomnia (participants are still eligible if they are taking traditional sleep medications)
- Those with untreated co-existing sleep conditions (e.g. sleep apnea)
- Those who have failed CBT for insomnia in the past

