## **7.3 Subject Confidentiality**

Subject confidentiality is held in strict trust by the research team. Subject medical record review will be limited to the just the elements needed to complete the study. The RA will also access the patient's full medical record, with read-only access, within the YNHH Epic electronic medical record (EMR) system. These data will not leave the Epic EMR system in any way, and are only being used to verify baseline eligibility. Data access to the YNHH Epic EMR will only be granted after all necessary trainings are complete and sign off is received from the Yale IRB and YNHH medical records department using the Yale New Haven Health System's Research Request for Medical Records Access form.

Each subject will be assigned a unique study number. A master list linking the unique study number to the human subject will be maintained in a secure encrypted folder on a password protected file.

All patient data will be collected, handled, and stored according the most rigorous accepted standards. Staff involved in the study will be appropriately trained to maximize data security and technical systems will meet or exceed requirements imposed by HIPAA. Sensitive information will always be encrypted in transit and at rest.

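### Section 6.3.3 settles eligibility by a looser rule than the 5.3.2 criteria and with inconsistent timing, so it does not ensure that excluded patients are kept out before randomization

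*Combined protocol and SAP*

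**What the plan says.** Section 5.3.2 requires a diagnosis of chronic insomnia. Among its exclusions are "Those with untreated co-existing sleep conditions (e.g. sleep apnea"), reported psychosis, schizophrenia or bipolar disorder, and medical disorders for which sleep restriction is contraindicated.

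Section 6.3.3 repeats that eligible patients must "have a diagnosis of chronic insomnia (see inclusion/exclusion criteria above in section 5.3.2"). It then gives the operating rule: "Eligibility will be determined by the sleep physician or coordinator stating that the patient is being seen for insomnia".

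On timing, 6.3.3 says "Patients will be identified by the sleep clinic coordinator and/or the sleep physician after their initial consult", but also that the research associate (RA) approaches them "while they are waiting for their sleep consult appointment/referral to see the sleep specialist". It puts the wait between enrollment and the specialist at up to 12 weeks. A second route is described as follows: "The RA will also reach out to patients on the waitlist for in-person CBT-I upon the sleep clinician's approval".

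Section 6.3.4 has the patient seen first by a sleep coordinator or a sleep physician. Either of them may deem the patient eligible and then contact the RA.

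Section 7.3 gives the RA read-only access to the full YNHH Epic record and says these data "are only being used to verify baseline eligibility". Section 3.2.1 tells a different story: "researchers are only getting access to patient data from the time of enrollment forward for 63 weeks for this study", with no open access to the whole record.

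**The concern.** The protocol lists detailed criteria and then says eligibility is decided by something weaker. A statement that someone is attending for insomnia shows neither chronicity nor the absence of any excluded condition, and a coordinator may make it.

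Two things are at stake. The first is who is studied: 6.1.1 describes the device as intended for adults with chronic insomnia, and the trial is meant to evaluate it in that population. The second is protection of participants: 3.2.1 says the intervention may ask people to restrict sleep, and 5.3.2 excludes patients with disorders for which that is contraindicated. If the operating rule lets such a patient through, the protocol's own safeguard has not been applied.

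**Working it through.** No figure in the plan depends on this rule, so there is nothing to reproduce. The check sets the sections side by side.

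**1. Rule against criteria.** Section 5.3.2 lists 7 inclusion and 7 exclusion criteria, 7 + 7 = 14. The 6.3.3 statement bears on one of them, the diagnosis, and only in part, because it does not speak to chronicity. It is silent on the other 13. The cross-reference to 5.3.2 says what an eligible patient must be. The quoted sentence says how that is decided. The two do not match, and no section describes a sign-off criterion by criterion.

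**2. Who and when.**

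| Source | Point at which the patient is identified or approached | Who judges |
|---|---|---|
| 6.3.3, identification | after the initial consult | coordinator and/or physician |
| 6.3.3, approach for consent | while waiting for the consult or specialist referral | physician or coordinator |
| 6.3.3, CBT-I waitlist | while on the waitlist | sleep clinician approves the outreach |
| 6.3.4 | after being seen initially at the Sleep Center | coordinator or physician |

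On the most favorable reading there is an initial contact followed by a wait for the specialist. Even then, the initial contact may involve only a coordinator. For the waitlist route, the clinician's approval is given for contacting the patient; it is not described as a check of the criteria.

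**3. What the 7.3 chart check adds.** It is a real second check and could apply several criteria. It has four limits:

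- It shows conditions already recorded, not ones that nobody has evaluated.
- It is described for the YNHH record only. Section 5.3.1 plans 50 patients there and 50 at Mayo, so no such check is described for 50/100 = 50% of the sample.
- It is not placed before randomization.
- It conflicts with 3.2.1. One section says the RA opens the full record; the other limits researchers to data from enrollment onward.

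**4. Whether a later step would catch an error.** None is described. Sleep apnea is self-reported as a covariate (6.4.4). Incoming questionnaire and device data are not reviewed by researchers (7.12). Stopping the intervention is limited to the patient's own choice (6.3.7). All analyses are intent-to-treat (6.4.1), so a patient randomized in error stays in the primary comparison. Intent-to-treat is sound in itself, but it means eligibility has to be settled before randomization.

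**5. Room for a check.** Section 6.3.1 places randomization on day 14 after enrollment with a window of +3 days, so 14 to 14 + 3 = 17 days are available without changing the schedule.

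**The case against.** The strongest reply is that one loose sentence is being read in isolation. The same paragraph says patients must have the diagnosis and points to 5.3.2. The rule names the physician as well as the coordinator. Waitlist patients are contacted only with a clinician's approval, and 7.3 provides a record review for exactly this purpose. A two-step pathway reconciles most of the timing text. The document is written largely from the Yale side and 7.9 says Mayo obtains its own IRB approval, so silence about a Mayo chart check does not show that there is none.

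Much of this stands, and it rules out several stronger readings that a reader might infer:

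- **That the criteria cannot be applied.** The documents do not support this. Sections 6.3.3 and 7.3 both give staff a basis for applying them; what is missing is assurance that they are applied.
- **That the later specialist visit is where insomnia or another disorder is diagnosed, before the primary outcome.** The primary ISI falls 2 + 9 = 11 weeks after enrollment, or (17 + 63)/7 = 11.4 weeks with the window, against a wait of up to 12 weeks. The visit could therefore often come first. But no section calls it diagnostic, and 6.3.3 describes it as follow-up.
- **That the planned effect size can be scaled down by an assumed share of ineligible patients.** The documents give no such share and no effect for these patients. In 6.4.2, d=0.52 is the detectable effect, put at one half to one third of effects seen before, which implies 0.52 × 2 = 1.04 to 0.52 × 3 = 1.56. Scaling 0.52 would treat a detectable effect as an expected one.

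The reply does not remove the conflict between the stated rule and the criteria, the open timing of the chart check, or the contradiction between 3.2.1 and 7.3.

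**Conclusion.** The point holds as a conflict within the protocol: the stated way of determining eligibility is weaker than the criteria it is meant to apply, and the text on timing and record access is inconsistent. Applied literally, it does not ensure that patients excluded by 5.3.2 are kept out before randomization.

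Confidence is high on the textual conflict. There is no basis for a number on the consequence: neither the share of ineligible patients nor the effect on ISI or power can be derived. The conclusion assumes that the 6.3.3 sentence is followed as written and that no site procedure outside these documents adds a fuller check. It is worth amending because the correction is cheap and bears on participant protection as well as on the study population.

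**What to change.** Replace the quoted sentence in 6.3.3 with wording such as:

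*Before randomization, at both sites, eligibility is confirmed and documented against each inclusion and exclusion criterion in Section 5.3.2, using the existing clinic evaluation and the medical record. The checklist names who confirms each criterion. The check excludes known conditions; it does not detect conditions that have not been evaluated.*

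Use the existing run-in and its +3-day window. Reconcile the timing sentences in 6.3.3 with each other and with 6.3.4, so that one sequence of first contact, approach and specialist visit is described. In 7.3, state that the record check covers both sites and precedes randomization. Correct 3.2.1 to agree with 7.3 that the full record is read to verify eligibility.

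Confirmation need not be reserved to a sleep physician by day 14. With specialist waits of up to 12 weeks, that could remove many enrolled patients, and a signature would still not rule out a condition nobody has evaluated.

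Cost: a protocol amendment, a short checklist, and a few enrolled patients found ineligible before randomization. No new test or visit is needed.

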#### 6.3.4 Enrollment

Patients with insomnia will be seen initially by a sleep coordinator or sleep physician at the Sleep Center. If deemed eligible for the study, the sleep coordinator or sleep physician will contact the Research Associate (RA) about the potential participant. If the RA is present in clinic, they will introduce themselves to the patient and provide additional information about the study. Should a clinician identify an eligible patient at a time when the RA is not present, the clinician will inform the patient about the study and ask if the patient would be willing to be contacted by the RA. If so, the clinician will email the RA, who will then contact the patient via phone and ask if they would like to participate in the study. If yes, the RA will attempt to arrange an in-person visit to conduct the consent and enrollment process. If an in-person visit is not possible, the RA will arrange a time for a Zoom call with the patient to complete all steps of consent and enrollment (minus the Fitbit set-up) via Zoom. The coordinator will then mail the Fitbit to the patient for arrival within 7 days.

Upon enrollment, patients will be asked to sign an electronic consent and link their electronic health records and share them with the research team. Patients will need to have their smartphone and any relevant phone account passwords at the time of enrollment. As part of the consent process, the RA will advise patients that they should contact their doctor or emergency services directly if they begin having new or worrying symptoms, exactly as the patient would have done so if they were not enrolled in our study.

Upon consent into the study, the patients will receive a Fitbit. For both arms of the study, Hugo will be used as a data collection platform as it aggregates data from multiple real-world data sources, thereby enabling the assessment of patient-reported outcomes, clinical outcomes, and healthcare utilization metrics. All participants will receive materials on sleep hygiene and healthy sleep tips. These sleep hygiene recommendations and healthy sleeping tips include behavioral information regarding getting a good night's sleep (e.g. setting a regular bed-time, getting out of bed if remaining awake, exercising regularly, not smoking). A full list of these tips can be found in **Appendix 1**. Patients will also receive a informational wallet card with study contact information (Appendix 8). Participants randomized to PEAR-003b will receive access to the therapeutic for 9

weeks a in addition to the sleep hygiene material. Post assessment data will be collected post intervention via diaries and questionnaires as outlined in the “Follow-up” section.

Because the Hugo platform obtains patient data through patient portals, all patients who connect will need a YNHH MyChart account. If the patient does not yet have a MyChart account, the RA will assist the patient in creating one. The RA will then assist the patient in linking their YNHH electronic health records to the Hugo platform as well as other health systems where they have received care by showing the study participant how to enter their patient portal credentials, provided that these health systems are connected to the Hugo platform.

Upon enrollment and following syncing of the Hugo and Fitbit devices (with assistance from the RA), patients in both study arms will complete a baseline assessment that will include questionnaires as well as 10 days of sleep diaries within a 14-day window. Questionnaires will relate to insomnia severity (ISI), depression (PHQ-8), daytime sleepiness (ESS), stress (PSS-10), health-related quality of life (SF-12) and anxiety (GAD-7). Please see **Appendix 2** for original paper versions of questionnaires. These PROMs will also be administered using the Hugo platform at 9-, 21-, 35-, and 61- weeks post-randomization. The RA will also ask patients to obtain credentials, if necessary, and connect portals to health systems where they receive care that are connected to Hugo but were unable to connect at enrollment. Patients will also receive a follow-up email from the RA that includes user guides for the Fitbit Inspire 2 (**see Appendix 3**). After the 14-day window, the patients will be randomized. Patients randomized to PEAR-003b will be contacted by the RA and will be guided through installing and initiating the CBT-I app.

The RA will collect the following data at enrollment:

- Number of people asked for study participation and number enrolled.
- Number of study participants who required assistance setting up YNHH portal.
- Number who had YNHH portal who could not be enrolled (e.g. because they had forgotten password, no space on mobile device, technical glitch, etc.).

If a patient refuses to participate, then we will note the number of people who refused. If the patient is agreeable, we will then administer a short questionnaire to understand their rationale for not participating in the study, to understand potential reasons for non-participation. We will also ask these people who chose not to participate about basic demographics, if they are willing to answer (age, sex, race/ethnicity, major co-morbidities, insurance status). Please see **Appendix 4** for questionnaire.

### 6.3.5 On Study Visits

All patients will be asked to use the Hugo platform and Fitbit wearable for the entire 63-week period. Those randomized to PEAR-003b will be asked to complete the 6 core modules in 9 weeks, and at completion will be asked to fill out a questionnaire via Hugo to determine their satisfaction with the process of answering queries and will provide the opportunity for them to offer comments and suggestions for improvement. Patients will be asked to charge their Fitbit for the minimum necessary time during the day and try to wear it for as much time as possible. We will cycle patient reminders about charging the Fitbit for continuous study use based on the anticipated battery life of the Fitbit wearable. Based on our prior experience conducting both SHUTi and Hugo projects, we anticipate being able to stream electronic health record and patient-generated data from the Fitbit into our researcher database using the Hugo platform. The enrollment visit is the only time patients will need to come in for an in-person visit. All subsequent visits will be completed at home. For all patient-reported outcome measures, we will query patients regarding whether they prefer a secure email link or text message link to receive questionnaires at baseline, 9, 21, 35, and 61 weeks. If patients do not respond to this prompt within 24 hours, they will receive an email reminder. Should there be still be no response after an additional 48 hours, the RA will follow up with the patient via phone to ask the patient to complete the unanswered survey.

Patients will be contacted by the RA via phone at 35 and 61 weeks to ascertain any new health systems in which they sought care and the Hugo platform will be checked to ensure that data from those health systems are included (and patients will be asked to link those health systems or provide data, as appropriate). Multiple attempts will be made to contact patients if they are not contacted on the first attempt. Patients will receive automatic reminders to complete questionnaires at 9, 21, 35, and 61 weeks post-randomization via email. Similarly, patients will receive automatic reminders to sync their Fitbit at these time points.

- **Enrollment Visit (in-person) [~3 hours total]:**
  - Informed Consent/study enrollment
  - Fitbit setup
  - Hugo account setup
  - Baseline Surveys: Baseline Questionnaire; ISI; PHQ-8; GAD-7; ESS; PSS-10; SF-12
  - Begin sleep diaries
- **Day 15 post-enrollment**
  - Patients are randomized by RA
  - Patients randomized to the PDT arm will be contacted by the RA and instructed on how to download and sign-up for Pear-003b.
- **Randomization through 9-week post-randomization**
  - Intervention Arm: Complete the Pear-003b PDT
  - Control Arm: Standard of Care
- **9-weeks post-randomization [~3 hours total]**

- Complete follow-up surveys: ISI; PHQ-8; GAD-7; ESS; PSS-10; SF-12
- Begin sleep diaries
- **21-weeks post-randomization [~3 hours total]**
  - Complete follow-up surveys: ISI; PHQ-8; GAD-7; ESS; PSS-10; SF-12
  - Begin sleep diaries
- **35-weeks post-randomization [~3 hours total]**
  - Complete follow-up surveys: ISI; PHQ-8; GAD-7; ESS; PSS-10; SF-12
  - Begin sleep diaries
- **61-weeks post-randomization [~3 hours total]**
  - Complete follow-up surveys: ISI; PHQ-8; GAD-7; ESS; PSS-10; SF-12
  - Begin final sleep diaries
  - Complete close-out questionnaire

